6.3.11 Other Safety Assessments

Physical Examination

Full physical examination will consist of assessment of head, eyes, ears, nose throat, mouth, cardiovascular, respiratory, digestive, urogenital, musculoskeletal, nervous/psycological, endocrine/metabolic, hematologic, dermatological, allergies, inmunological and other. The observed values for the physical examination will be recorded in the eCRF by the investigator as "normal" or "abnormal" and if abnormal, assessed as "clinically significant" or "not clinically significant".

The Investigator will perform full physical examinations at the Screening visit and at the Early Termination visit.

Date: 09-JUL-2021

Sponsor: Laboratorios Salvat, S.A. Study Code: CLOBOF3-16IA01 NCT No.: NCT04246801

The investigator will perform physical examination following the usual standards of patients' examination at each study site.

Eye Examination

Pupil function, ocular alignment and motility, visual field by confrontation test, and anterior vitreous will be assessed for normality and clinically significance at the Screening visit and at the Early Termination visits.

Vital Signs

Vital signs will be assessed 15 minutes before any ocular assessment and at least 30±10 minutes before the first study medication administration. For all vital signs parameters (systolic and diastolic blood pressure, heart rate and body temperature) summary statistics will be produced for observed values by visit.

Vital signs data will be listed by patient. All clinically significant abnormal values will be flagged in this listing.

Indirect Ophthalmoscopy

Vitreous humor, central retina, peripheral retina, optic nerve disc and retinal vasculature will be assessed for normality and clinically significance at the Screening, Baseline, Visit 4, Visit 5 and at the Early Termination visit.

Outputs will be based on the SAF.

6.4 Level of Significance, Multiple Comparisons and Multiplicity

All statistical hypotheses will be two-sided and will be performed using a 5% significance level. No adjustment for multiple comparisons or corrections for multiplicity are foreseen.

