2.2 Rationale for the Study

Cataract surgery is one of the most common surgical procedures performed worldwide. In fact, in 2017, 3.8 million cataracts procedures were performed in the US.

Despite of surgical advances, pain and inflammation after ophthalmic surgery continues to be a burden on both patients and physicians. The treatment of postoperative pain is essential for hospitalized patients, but it is even more important for patients who are treated on an outpatient basis.

Also, pain after ophthalmic surgery may be considered a sign of a possible complication. Severe pain is assumed to be a sign of postoperative inflammation or infection, making it a concern for both patient and physician. However, a surgery without perioperative complications may also be associated with significant postoperative pain during the early

recovery. Thus, appropriate counseling and pain management should be provided to improve quality of life.

Clobetasol propionate ophthalmic nanoemulsion 0.05% will be administered as a topical ophthalmic nanoemulsion.

Patients are expected to self-administer one drop of either clobetasol propionate ophthalmic nanoemulsion 0.05% or placebo control QID.

Direct instillation is the most efficient method for delivery to the ocular surface and is an accepted and widely used method for topical application to the eye. This study will examine effect and tolerability for 14 days of clobetasol propionate ophthalmic nanoemulsion 0.05% dosed QID.

This study is being conducted to support an application for approval to market clobetasol propionate ophthalmic nanoemulsion 0.05% in the US for the indication of inflammation and pain after ocular surgery. The reference (comparator) product in this study, the vehicle, is expected to provide a lower efficacy rate when compared to clobetasol 5%.

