9.1.10 Primary Analysis

The aim of the primary analysis of this study is to assess the superiority of clobetasol propionate ophthalmic nanoemulsion 0.05% compared to placebo with respect to the primary endpoint in the FAS.

The primary analysis will be based on a single study eye for each patient. Each patient's study eye will be defined as the surgery eye.

The test will be the proportion of study eyes with complete clearing of anterior chamber cells (count cell = 0) at Visit 3 (Day 8 ± 1 day) without receiving rescue medication as compared between clobetasol propionate ophthalmic nanoemulsion 0.05% dosed QID and placebo dosed QID using the chi square statistic.

The PP population set will be also tested to confirm the robustness of the primary analysis.

The primary estimand (efficacy estimand) will be defined as the effect of the randomized treatments in all subjects meeting selection criteria assuming continuation of randomized treatments for the duration of the study regardless of actual compliance.

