9.1.11 Key Secondary Analysis

The aim of the key secondary analysis of this study is to assess the superiority of clobetasol propionate ophthalmic nanoemulsion 0.05% compared to placebo with respect to the key secondary endpoint in the FAS.

The key secondary analysis will be based on a single study eye for each patient. Each patient's study eye will be defined as the surgery eye.

The test will be the proportion of study eyes with no pain (pain = 0) at Visit 3 (Day 8 ± 1 day) without receiving rescue medication as compared between clobetasol propionate ophthalmic nanoemulsion 0.05% dosed QID and placebo dosed QID using the chi square statistic.

The PP population set will be also tested to confirm the robustness of the key secondary analysis.

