9.2 Changes in Statistical Methods

Any deviation(s) from the original statistical analysis plan (as described in the study protocol or in the SAP) will be described and justified in a protocol amendment and/or in a revised SAP and/or in the final report, as appropriate.

If, after the study has begun, but prior to any unmasking, changes are made to primary hypothesis, or the statistical methods related to this hypothesis, then the protocol will be amended (consistent with ICH Guideline E-9). Changes to other non-confirmatory analyses made after the protocol has been finalized, along with an explanation as to when and why they occurred, will be listed in the CSR for the study. Post hoc exploratory analyses will be clearly identified in the CSR.

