2.2 Secondary Objectives

Key secondary objective

Efficacy:

• To assess the effect of clobetasol propionate ophthalmic nanoemulsion 0.05% on eye pain associated with cataract surgery after one week of treatment.

Other secondary objectives

Efficacy:

- To assess the effect of clobetasol propionate ophthalmic nanoemulsion 0.05% on ocular inflammation associated with cataract surgery
- To assess the effect of clobetasol propionate ophthalmic nanoemulsion 0.05% on eye pain and on eye discomfort associated with cataract surgery

Safety:

 To evaluate the safety and tolerability of clobetasol propionate ophthalmic nanoemulsion 0.05%

Sponsor: Laboratorios Salvat, S.A. Study Code: CLOBOF3-16IA01 NCT No.: NCT04246801

3 **ENDPOINTS**

3.1 **Primary Efficacy Endpoint**

Proportion of patients with anterior chamber cell grade of "0" (absence of cells) compared to placebo at Day 8.

Anterior chamber cell grade will be assessed by the investigator during slit-lamp examination and will be graded on an adapted 6-point scale proposed by the Standardization of Uveitis Nomenclature (SUN) working group (Table 1).

Calla in field*

Table 1. Grading scheme for anterior chamber cells

^{*}Field size is a 1mm by 1 mm slit beam

[figure not shown]
Grade	Cells in field*			
0	0			
0.5+	1-5			
1+	6-15			
2+	16-25			
3+	26-50			
4+	>50			
*Field size in a dame but dame alik beare				

3.2 **Secondary Efficacy Endpoints**

Key secondary efficacy endpoint

Proportion of patients with VAS pain score of "0" (no eye pain) compared to placebo at Day 8.

Eye pain score will be assessed by the patient before any ocular examination and will be scored by ticking on a continuous scale comprised of a 10 cm horizontal line anchored by two verbal descriptions: "no eye pain" (score of 0) and "worst imaginable eye pain" (score of 10).

The records to be considered are those whose date coincides with the visit to be analyzed for VAS pain score except in model to analyze the change over time in the VAS pain score reported every day compared to placebo.

Proportion of patients with anterior chamber cell grade of "0" compared to placebo at Day 3, Day 15 and Day 29.

Version: Final 3 Study Code: CLOBOF3-16IA01
Date: 09-JUL-2021 NCT No.: NCT04246801

• Change from Baseline to Day 3, Day 8, Day 15 and Day 29 compared to placebo in the proportion of patients with different anterior chamber cell grades.

Sponsor: Laboratorios Salvat, S.A.

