6.3.5 Primary Efficacy analysis

The primary efficacy endpoint in this clinical trial is the proportion of patients with anterior chamber cell grade of "0" (absence of cells) compared to placebo at Day 8.

The statistical hypothesis that will be tested for primary efficacy is described as:

- Null Hypothesis (H_0): The difference in proportion of patients with anterior chamber cell grade of "0" at Day 8 between treatment regimes = 0.
- Alternative Hypothesis (H₁): The difference in proportion of patients with anterior chamber cell grade of "0" at Day 8 between treatment regimes ≠ 0.

The aim of the primary analysis of this study is to assess the superiority of clobetasol propionate ophthalmic nanoemulsion 0.05% compared to placebo with respect to the primary efficacy endpoint. The primary analysis will be based on a single study eye for each patient. Each patient's study eye will be defined as the surgery eye.

A Chi-Square test will be employed to test the proportion of study eyes with complete clearing of anterior chamber cells (count cell = 0) at Visit 3 (Day 8 \pm 1 day) without receiving rescue medication as compared between clobetasol propionate ophthalmic nanoemulsion 0.05% dosed QID and placebo dosed QID. The proportion of eyes with absence of cells (anterior chamber cell grade=0) together with its 95% confidence interval (CI) will be presented. Analysis will be conducted both in FAS and PP to test the robustness of the results.

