6.3.6.2 Secondary Analysis

The secondary efficacy endpoints are described in Section 3.2. All secondary efficacy endpoints defined in this section will be analysed as exploratory.

For categorical variables, a summary of these endpoints will be presented at each specified timepoint by treatment group and will include the number and percentage of each category with the 95% CI. A chi-square test or Fisher Exact test, as appropriate will be performed to compare proportions between treatments at each timepoint.

For continuous variables: VAS photophia, Snellen best-corrected visual acuity (BCVA) score and VAS pain score, a summary of these endpoints will be presented at each specified timepoint by treatment group. Change from baseline will be derived and presented in the same way.

For variables: Anterior chamber cell grades, anterior chamber flare grades, severity of signs of ocular inflammation and eye discomfort grades categorical and continuous summary statistics will be presented, changes from baseline will also be derived and will be presented as increase, decrease or not change table. In the same way, a table with 2 categories: Improvement and no improvement (increase+no change) will be presented. A chi-square test or Fisher Exact test will be performed to compare proportions between treatments:

Change from baseline to Day 3		
Anterior Chamber Cell Grade	IMP	Placebo
Decrease (Improvement)	n (%)	n (%)
No change	n (%)	n (%)
Increase (Worsening)	n (%)	n (%)
P value chi-square or Fisher	p-v	value
Improvement	n (%)	n (%)
No Improvement	n (%)	n (%)
	p-v	/alue

No Improvement = increase + no change

For the variables mentioned above, to see the proportion of patients with different grades, a descriptive table like the following will also be built, no statistical inference will be made:

Grade	IMP			Placebo		
Grade	Baseline	Day X	Change	Baseline	Day X	Change
0	n (%)	n (%)	(%)	n (%)	n (%)	(%)

Date: |09-JUL-2021|

Sponsor: Laboratorios Salvat, S.A. Study Code: CLOBOF3-16IA01 NCT No.: NCT04246801

0.5+	n (%)	n (%)	(%)	n (%)	n (%)	(%)
1+	n (%)	n (%)	(%)	n (%)	n (%)	(%)
2+	n (%)	n (%)	(%)	n (%)	n (%)	(%)
3+	n (%)	n (%)	(%)	n (%)	n (%)	(%)
4+	n (%)	n (%)	(%)	n (%)	n (%)	(%)

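### The SAP foresees no multiplicity control, neither document orders the cell-clearing and pain superiority tests, and the status of the pain test is unclear

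*SAP*

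**What the plan says.** Protocol 9.1.10 states: "The aim of the primary analysis of this study is to assess the superiority of clobetasol propionate ophthalmic nanoemulsion 0.05% compared to placebo". Protocol 9.1.11 uses the same form for pain: "The aim of the key secondary analysis of this study is to assess the superiority of clobetasol propionate ophthalmic nanoemulsion 0.05% compared to placebo". Both analyses are in the FAS at Visit 3, and both use a chi-square test of responders without rescue. Protocol 9.1 sets two-sided alpha at 0.05 for every test unless stated otherwise, and nothing is stated otherwise for these two.

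SAP 6.4 repeats the two-sided 5% level and adds: "No adjustment for multiple comparisons or corrections for multiplicity are foreseen".

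Protocol 2.2 says that the trial supports a marketing application "in the US for the indication of inflammation and pain after ocular surgery".

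On hypotheses, SAP 6.3.5 introduces H0 and H1 with "The statistical hypothesis that will be tested for primary efficacy is described as" and gives them for cell clearing only. SAP 6.3.6.1 describes the pain test without a hypothesis or a superiority aim. SAP 6.3.6.2 first points to Section 3.2 for the secondary endpoints and then says: "All secondary efficacy endpoints defined in this section will be analysed as exploratory". Section 3.2 opens with the entry "Key secondary efficacy endpoint", which is VAS pain of 0 at Day 8.

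**The concern.** Pain is half of the intended indication, so its test needs a defined role. Two questions have no answer in the text.

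- **Is the pain test confirmatory?** Protocol 9.1.11 suggests that it is. SAP 6.3.6.2, read through its pointer to Section 3.2, suggests that it is not. SAP 6.1 says that the SAP supersedes the protocol's statistical methods, so the protocol's superiority aim does not settle the matter.
- **May pain be claimed if cell clearing fails?** Nothing forbids it. The names primary and key secondary hint at an order, but neither document turns them into a testing rule. SAP 6.4 is where such a rule would stand, and it states that there is no correction.

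Followed to the letter, the plan allows a pain claim at the full 0.05 after a failed primary. The error rate across the two tests is then no longer held at 5%. Two matters are not in dispute: the FAS is clearly the primary population, and SAP 6.1 presents the 0-0.2 cm and 0-0.4 cm pain cut-offs as consistency checks.

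**Working it through.** **Inputs from the documents.** Two-sided alpha 0.05 for each test (Protocol 9.1, SAP 6.4). Assumed cell clearing 0.22 against 0.07, 80% power, 202 evaluable, 210 randomized as 140/70 (Protocol 9.1.1, SAP 4.2).

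**Assumptions.** The documents give neither the correlation between the two test statistics nor a Day 8 pain-free rate. Correlation is varied from 0 to 0.7 and the null pain-free rate from 30% to 55%. Null cell clearing is varied from 7% to 22%.

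**Step 1: the plan's own sample size.** With 2:1 allocation the pooled rate is (2 × 0.22 + 0.07)/3 = 0.17. At N = 202 the standard error is 0.0561 under the null and 0.0473 under the alternative. Power = Φ((0.15 − 1.96 × 0.0561)/0.0473) = 80.2%. The odds ratio (0.22/0.78)/(0.07/0.93) = 3.747 also reproduces. The sample size is sound, and it rests on cell clearing alone.

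**Step 2: family-wise error with both nulls true, if a win on either endpoint counts.**

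- Upper bound: 0.05 + 0.05 = 0.10.
- Independent tests: 1 − 0.95² = 0.0975.
- Benefit direction only, independent: 1 − 0.975² = 0.0494, against 0.025 for one test.
- Correlated tests, from a bivariate normal with critical value 1.96:

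| Correlation | Two-sided | Benefit only |
|---|---|---|
| 0 | 9.75% | 4.9% |
| 0.3 | 9.5% | 4.8% |
| 0.5 | 9.1% | 4.5% |
| 0.7 | 8.4% | 4.2% |

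**Step 3: exact check of the uncorrected chi-square at 140/70.** The exact two-sided size for cell clearing is 0.0468 at a null rate of 7% and 0.0507 at 22%. For pain it is 0.0503 at 30%, 0.0517 at 40% and 0.0508 at 55%. Treating the endpoints as independent, the lowest combination is 1 − (1 − 0.0468)(1 − 0.0503) = 9.5% and the highest is 1 − (1 − 0.0507)(1 − 0.0517) = 10.0%. Counting benefit only, the range is 4.4% to 4.8%.

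**Step 4: the alternatives.** Under a fixed sequence the error across both tests is at most 5%, and the primary keeps its 0.05. A Bonferroni split at 0.025 each also controls the error (1 − 0.975² = 4.9% if independent), but primary power at N = 202 falls to 69.6%. Restoring 80% would take about 246 evaluable and 257 randomized patients.

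**Step 5: how often the fixed sequence would stop before pain.** At the planned 80% power this is 20% of trials. Exact power at 140/70 is 83.4%, which gives 17%. If the planned 4% dropout is counted as failure in both arms (0.2112 against 0.0672), exact power is 81.4%, which gives 19%.

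**The case against.** The strongest reply is that the plan has only one confirmatory test, so there is nothing to adjust. There is one primary objective, the sample size rests on it alone, and H0 and H1 are stated for it alone. Protocol 9.2 contrasts changes to the primary hypothesis with "Changes to other non-confirmatory analyses made after the protocol has been finalized", which can be read as placing everything else outside the confirmatory set. On that reading no error rate is inflated. But Protocol 9.2 does not name pain, and the reading conflicts with the superiority aim in Protocol 9.1.11. One of the two texts has to give way.

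A second reply is that the indication is joint. If inflammation and pain are claimed only when both tests succeed, the chance of a false joint claim is at most 5% without adjustment. That is correct. However, no passage says that both must succeed, just as none says that either will do.

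A third reply is that the exploratory sentence stands in SAP 6.3.6.2, after a separate subsection for the key secondary, and that the output list in SAP 8.1 also gives the pain endpoint its own block. It is natural, then, to read pain as outside the exploratory label. This is a fair reading, but the sentence directly follows a pointer to Section 3.2, which includes the key secondary. If this reading is right, pain becomes a second unadjusted superiority test and the missing order remains.

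What stands: the inflation figures hold only under an either-endpoint rule, and the primary conclusion is not affected.

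**Conclusion.** The concern holds. The SAP rules out correction, the protocol gives two endpoints the same superiority aim at 0.05, and neither document orders the tests. If a win on either endpoint counts and both nulls are true, the two-sided family-wise error is about 8.4% to 9.75% over assumed correlations of 0.7 down to 0, and 10% at most. False claims of benefit are about 4.2% to 4.9%, against 2.5% for one test. There is no inflation if only the primary is confirmatory, or if pain is tested only after the primary succeeds. The documents do not say which case applies. The primary test stays at 5% throughout. This should be corrected because the pain claim has no defined inferential basis, but it is not a fault in the primary analysis.

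**What to change.** In SAP 6.4, replace the no-adjustment statement for these two endpoints with a fixed sequence:

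1. Test cell grade 0 at Day 8 in the FAS at two-sided 0.05.
2. Only if that is significant in favour of clobetasol, test VAS pain of 0 at Day 8 in the FAS at two-sided 0.05.

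In SAP 6.3.6.2, state that the exploratory label does not cover the key secondary endpoint. State also that the FAS non-RM, PP and 0-0.2 cm and 0-0.4 cm pain results are supportive, with nominal p-values. SAP 5 runs both main endpoints in the FAS non-RM set as well, so the text should say that only the FAS tests are in the sequence. Align Protocol 9.1.11 with this. If the sponsor instead intends pain to be exploratory, that should be stated and Protocol 9.1.11 reconciled with it.

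The SAP change is a few sentences. The protocol change needs an amendment, although SAP 6.1 lets the SAP text govern in the meantime. Sample size (202 evaluable, 210 randomized) and primary power do not change. The cost is that pain cannot be claimed if the primary fails, about 17 to 20% of trials under the protocol's assumed rates.

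The rule has to be fixed before unmasking. The SAP is dated 09-JUL-2021 and the last visit was planned for 4Q 2020; the documents do not show whether unmasking had taken place. If it had, the order can only be reported as chosen afterwards.

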6.5 Adjustment for Covariates

Baseline value will be used as a covariate in the MMRM analyses for the continuous secondary efficacy endpoints (see Section 6.3.6).

6.6 Handling of Dropouts and Missing Data

No missing imputation methods are foreseen. As described in the CSP, any missing, unused, or spurious data will be noted in the final Clinical Study Report (CSR) and presented in the data listings.

In all listings, missing or incomplete dates should be left as they have been recorded. However, for calculation / sorting / assignation based on dates, the following method will be used, in the event that any date is incomplete after Data Management processing and this date needs to be used for calculation:

- if no field is available: no imputation will be performed,
- if only the year is available: Day "01" and month of "July" will be imputed,
- if the month and year are available: Day "15" will be imputed.

Date: 09-JUL-2021 NCT No.: NCT04246801

Sponsor: Laboratorios Salvat, S.A. Study Code: CLOBOF3-16IA01

6.7 Multicentre Studies

As stated in the CSP, none of the analyses will be adjusted by study center.

6.8 Examination of Subgroups

NA

6.9 Interim Analysis

No formal Interim Analysis is foreseen for this study.

6.10 Reporting Conventions

P-values ≥0.0001 will be reported to four (4) decimal places; p-values less than 0.0001 will be reported as <0.0001. The mean and median will be displayed to one decimal place greater than the original value and the measure of variability (e.g., standard deviation) will be displayed to two decimal places greater than the original value.

8 LIST OF OUTPUT

8.1 Tables to be produced for the Clinical Study Report (Section 14 according to ICH E3)

Demographic data and baseline characteristics will be showed stratifying by treatment group (IMP and placebo) and overall.

Efficacy and safety analysis tables will be showed stratifying by treatment group, as well as each timepoint, as applicable.

For continuous variables, summary statistics will be included in the MMRM tables.

14.1 DEMOGRAPHIC DATA

Patient disposition

Table	Title	Pop	Top.Line
14.1.1	Patient disposition: Number of patients in each analysis set and reason for exclusion	ALL	Х
14.1.2	Number of patients by visit	ALL	
14.1.3	Reason for finish the study prematurely	ALL	

Demographic and baseline characteristics

Table	Title	Pop	Top.Line
14.1.4	Demographics	SAF	
14.1.5	Urine pregnancy test	SAF	
14.1.6	Cataract diagnosis	SAF	
14.1.7	Relevant Medical History	SAF	

